### 7.5.2 Visit 1b: Pair 1 Dispensing Visit

*Dispensing visit should occur on same day as Visit 1a. In the event of unacceptable short-term slit-lamp findings, e.g. excessive corneal staining, Visit 1b may be conducted on a different day to Visit 1a, where slit lamp biomicroscopy should be conducted again to confirm eligibility.*

- The first study pair of contact lenses will be selected by the investigator according to the randomization table (Appendix 3) for insertion by the subjects. Subjects will be dispensed the lens power nearest to their vertex corrected refractive error requirement. The lens powers of Pair 1 and Pair 2 will be matched.
- Lenses should be allowed to settle for 10 minutes.
- An initial fit assessment will be made to ensure lens fit is acceptable (Y/N). The subject should be discontinued and exited if the lens fit is found unacceptable and the primary reason for poor fit recorded on the CRF and video footage of the fit collected.
- Monocular spherical over-refraction (SOR) will be conducted to determine if a different lens power is required.
- Monocular and binocular **HIHC** and **HILC** distance logMAR visual acuities will be recorded (SOR will be used if the subject is wearing monovision).
- Final lenses will be inserted and allowed to settle for a further 10 minutes, if applicable.
- Subjective responses will be collected per the Post-Settling Questionnaire (Appendix 4), including:
  - Lens insertion
  - Comfort satisfaction & comfort rating (6-point Likert & 100-point scales)
- A gross assessment of lens surface will be made:
  - Overall lens surface quality/wettability (acceptable / unacceptable)
  - Comments, if applicable

- Lens fit will then be assessed and graded according to the guidelines detailed in CVI Grading scales (see Appendix 2).
  - Lens centration (0.1mm steps)
  - Corneal coverage (Yes / No / Borderline)
  - Post-blink movement (0.1mm steps)
  - Mobility rating (0.50 steps)
  - Overall lens movement (-2 to +2 scale)
  - Overall lens fit acceptance and investigator reason, if unacceptable (0.25 steps). Video will be recorded in the event of poor fit.
- Information for Safety for contact lens wear during the clinical study as described in the section 5.6 will be reviewed with each subject.
- The subject must have a minimum of 8 hours of exposure in the lens on at least 2 days before their next study visit.
- The subject will be dispensed adequate lenses (including spares) to last them until the next study visit.

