### 9.1 Statistical Hypothesis

---

The primary statistical hypothesis is that the comfort performance with the Test lens will demonstrate statistical equivalence to the comparator (Control) lens over two days of lens wear.

The secondary statistical hypothesis is that the vision performance with the Test lens will demonstrate statistical equivalence to the comparator (Control) lens over two days of lens wear.

*Other hypotheses:*

The lens fit performance with the Test lens will demonstrate statistical equivalence to the comparator (Control) lens over two days of lens wear.

The lens handling performance with the Test lens will demonstrate statistical equivalence to the comparator (Control) lens over two days of lens wear.

Corneal staining performance with the Test lens will demonstrate statistical equivalence to the comparator (Control) lens over two days of lens wear.

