#### 9.2.1 Primary Hypothesis

Table 3 below shows the sample size estimations for a paired t-test ( $\alpha = 0.05$ ) in order to detect differences in mean ocular comfort scores between Test vs. Control conditions. Assuming a standard deviation of a paired difference of 13 points, a sample size of 44 subjects provides adequate power to detect a potential paired difference of 7 points on a 0-100 point scale.

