### **9.2.2 Secondary Hypothesis**

Assuming a standard deviation of a paired difference of 0.1 logMAR, a sample size of 27 subjects provides adequate power to detect a potential paired difference of 0.05 logMAR in mean vision scores between Test vs. Control conditions for a paired t-test (alpha = 0.05).

Therefore, a sample size of approximately 45 completing subjects is sufficient for this study.

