## **9.3 Statistical Analysis**

---

Summary statistics [may/will] be produced (e.g. mean, standard deviation). Paired t-test will be used to compare slit lamp biomicroscopy, lens fit and subjective scores between study lens types. Where applicable, Repeated Measures Analysis of Variance (ANOVA) or paired analysis will be used to compare the variables between study visits. The critical alpha level for statistical significance will be set at  $p \leq 0.05$ , with adjustment for multiple comparisons.

Equivalence testing will be undertaken to first determine statistical non-inferiority and then equivalence (if applicable) to the comparator (Control) lens, to confirm the primary and secondary hypotheses.

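### The paired t-test that Section 9.3 assigns to all of lens fit does not suit two fit items: three-category corneal coverage and, if 0 is the optimum, the signed -2 to +2 movement score

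*Combined protocol and SAP*

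**What the plan says.** Section 9.3 names one method for comparing fit between the lenses: "Paired t-test will be used to compare slit lamp biomicroscopy, lens fit and subjective scores between study lens types". It makes no exception for any fit item. The repeated-measures or paired alternative in the same section is for comparisons between study visits.

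Sections 7.5.2 to 7.5.4 grade lens fit on six items:

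- centration (0.1 mm steps)
- "Corneal coverage (Yes / No / Borderline"
- post-blink movement (0.1 mm steps)
- mobility rating (0.50 steps)
- "Overall lens movement (-2 to +2 scale"
- overall fit acceptance (0.25 steps)

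The grading rules are referred to Appendix 2, whose scales are not shown.

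Section 9.1 claims equivalence for fit: "The lens fit performance with the Test lens will demonstrate statistical equivalence to the comparator (Control) lens over two days of lens wear". It names no fit variable, time point or margin, and places this claim under other hypotheses, although Section 7.1 lists lens fit as a secondary endpoint. Section 9.3 promises equivalence testing "to confirm the primary and secondary hypotheses".

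**The concern.** A paired t-test compares means, so the score must have a mean that tracks quality of fit. Neither item clearly does.

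Coverage is a label. It has no mean until someone assigns numbers, and the plan assigns none.

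Movement is scored on a signed range that is symmetric about zero. The natural reading is that 0 is optimal and the two ends are too tight and too loose. On that reading, a subject at -1 and a subject at +1 are both fitted worse than one at 0, yet their average equals his. A lens with more misfit in both directions would show no mean difference on this item.

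Equivalent lens fit is one of the user requirements in Section 1, and the study is described as confirmatory design validation. Table 1 gives the lenses different diameters (14.10 and 14.00 mm), so fit is a genuine question. At stake is the reading of these two fit items.

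**Working it through.** **What the plan supplies.** The documents give no standard deviation, margin or power for lens fit, so there is no fit figure to reproduce. As a check on the paired t-test calculation, all 12 cells of Table 3 (comfort, n = 20, two-sided 0.05) come back within 1 point; for example, SD 10 gives 56.5, 88.9 and 98.9% against the stated 56, 89 and 99%.

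**Inputs.**

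- From the documents: about 45 completers (Section 9.2.2), alpha 0.05 (Section 9.3) and the two scales (Section 7.5.2).
- Assumed: 0 is the movement optimum; one score per subject and lens; Test and Control scores independent; the score distributions; the equivalence margins. The t-test is taken as two-sided and equivalence as two one-sided tests at 0.05 (90% interval).

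**Coverage.** Suppose 35 of 45 subjects are Yes with both lenses, and 10 are Borderline with Control and No with Test. The mean of Test minus Control is then:

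| Coding | Mean difference |
|---|---|
| Yes 1, No 2, Borderline 3 (listed order) | 10 × (2 − 3) / 45 = −0.22 |
| Yes 0, Borderline 1, No 2 | 10 × (2 − 1) / 45 = +0.22 |
| Yes 0, anything else 1 | 0 |

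The same data give three answers, two of them with opposite signs. This needs no assumption about Appendix 2.

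**Movement, one data set.** Let Control be 0 in all 45 subjects, and Test be -1 in 11, +1 in 11 and 0 in 23. The signed mean difference is (11 − 11)/45 = 0.00, with SD 0.707, p = 1.00 and a 90% interval of -0.18 to 0.18. On distance from 0 the mean difference is 22/45 = 0.49, with p < 0.000001.

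**Movement, repeated trials.** Control scores -1, 0, +1 in 5, 90, 5%. Test scores -2, -1, 0, +1, +2 in 10, 15, 50, 15, 10%.

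*Signed score.*

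- Mean difference: 0.
- Variance of the difference: 0.10 + (0.30 × 1 + 0.20 × 4) = 1.20.
- Standard error: √(1.20/45) = 0.163.
- 90% half-width: 1.680 × 0.163 = 0.274.
- Equivalence at ±0.5 needs an observed mean within 0.5 − 0.274 = 0.226 of zero, which is 1.38 standard errors, so the chance is about 83%.
- At ±0.25 the typical half-width already exceeds the margin, so equivalence rarely passes.

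*Distance from 0.*

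- Mean difference: (0.30 × 1 + 0.20 × 2) − 0.10 = 0.60.
- Variance: (1.10 − 0.49) + (0.10 − 0.01) = 0.70.
- Standard error: √(0.70/45) = 0.125.
- Ratio: 0.60/0.125 = 4.8, against a critical value of 2.02.

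Simulation agrees, and gives these results for two further patterns of Test scores with the same Control:

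| Test pattern | Score | t-test significant | Equivalence at ±0.5 | Equivalence at ±0.25 |
|---|---|---|---|---|
| 10/15/50/15/10% | signed | 5% | 83% | 2% |
| | distance | 99.9% | 1% | under 0.1% |
| 0/25/50/25/0% | signed | 5% | 99% | 37% |
| | distance | 99% | 29% | under 0.1% |
| 0/5/45/50/0% (one direction) | signed | 99% | 11% | under 0.1% |
| | distance | 99.8% | 13% | under 0.1% |

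When misfit is symmetric, the signed t-test flags no more trials than its 5% error rate. When the shift goes one way, it works.

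**The case against.** **The anchors are unseen.** That 0 is the optimum is inferred from the symmetric range. This stands: the movement limb is conditional on Appendix 2. The coverage limb is not.

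**Other items could show worse fit.** Movement is one of six items, and overall fit acceptance is graded at every fit assessment. A reader might infer that a worse-fitting lens would be declared equivalent overall. The documents do not support that: nothing says the fit conclusion rests on the movement score. Equally, no item is designated as the fit endpoint, so none is a pre-specified safeguard.

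**The equivalence result depends on the margin.** A reader might take the 83% pass rate as the risk. In the same scenario it is about 56% at ±0.4, 14% at ±0.3 and 2% at ±0.25, because wider spread widens the interval. A tight margin would give partial protection. The plan states no margin, and it ties equivalence testing to the primary and secondary hypotheses while Section 9.1 lists fit among the others. The t-test is the only method clearly assigned to fit.

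**The illustration is severe.** It puts 20% of Test scores at the ends of the scale. Subjects whose initial fit is unacceptable leave before graded assessment (Section 7.5.2 and the Pair 2 dispensing procedures), which may thin out such scores. Table 1 gives both lenses the same base curve and water content, so nothing there predicts large misfit in both directions. This limits how likely the scenario is. The milder pattern, with no score beyond ±1, still leaves the t-test at about 5%.

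**Lens surface.** A reader might infer that the t-test also covers surface quality (acceptable or unacceptable). It does not: Sections 7.5.2 to 7.5.4 list surface as a separate gross assessment, and Section 9.3 does not assign the test to it.

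**Conclusion.** The point holds for two fit items. For corneal coverage the stated test has no defined result, because its size and sign depend on an unstated coding. For overall movement, if 0 is the optimum and misfit occurs in both directions, the signed t-test cannot see it: about 5% of trials are flagged against over 99% on distance from the optimum, with 45 subjects and optimal movement falling from 90% to 50%. The score distributions and margins are assumptions, and a one-directional shift would be found.

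The documents do not support a conclusion that the overall lens-fit requirement would be wrongly met, or that the primary comfort result is affected. The change is worth making before the data are analysed: it replaces an unsuitable stated method with a suitable one, at little cost.

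**What to change.** In Section 9.3:

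- **Overall movement.** Analyse distance from the optimum defined in Appendix 2, or the paired proportion of subjects at that optimum. Report the tight and loose distributions by lens. If Appendix 2 shows that 0 is not an interior optimum, this clause changes and the next one stands.
- **Corneal coverage.** Analyse the paired proportion with full coverage (Yes versus Borderline or No) by McNemar's test, with a confidence interval for the paired difference. Tabulate all three categories by lens.
- **Other fit items.** Keep the paired t-test for items whose scale has no interior optimum according to Appendix 2, and name them.

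The cost is a few sentences and minor programming, with no new data, visits or subjects. The downside is some loss of information from dichotomising coverage: in the example above, 10 subjects moving from Borderline to No would not change the Yes proportion. The three-category table is there to show such a shift.

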### 7.5.3 Visit 2: Pair 1 Follow-up Visit 2 days (+2 days) & Pair 2 Dispensing

*Subjects will be asked to wear lenses for at least 3 hours prior to the visit appointment.*

- The following information will be collected from the subject by the investigator:
  - Wear time at visit (hours).
  - Time of insertion and removal daily since last visit, (to calculate average time and maximum wear time (hours)).
  - Time of day lenses become uncomfortable, if at all, i.e. average comfortable wear time (hours).
- Subjective responses will be collected per the Follow-up Questionnaire (Appendix 5), including:
  - Overall satisfaction (6-point Likert & 100-point scales)
  - Comfort & comfort rating (6-point Likert & 100-point scales)
  - Comfort (insertion) (6-point Likert & 100-point scales)
  - Comfort (end of day) (6-point Likert & 100-point scales)
  - Dryness (freq/severity/bothersomeness) (5-point Likert scales)
  - Stinging/burning (freq/severity/bothersomeness) (5-point Likert scales)
  - Itchiness (freq/severity/bothersomeness) (5-point Likert scales)
  - Scratchy/gritty (freq/severity/bothersomeness) (5-point Likert scales)
  - Lens movement/awareness (freq/severity/bothersomeness) (5-point Likert scales)
  - Handling (6-point Likert & 100-point scales)

- Insertion (freq/severity/bothersomeness) (5-point Likert scales)
  - Removal (freq/severity/bothersomeness) (5-point Likert scales)
  - Lens holding/handling (freq/severity/bothersomeness) (5-point Likert scales)
- Vision (6-point Likert & 100-point scales)
  - Driving at night (6-point Likert & 100-point scales)
- Monocular and binocular **HIHC** and **HILC** distance logMAR visual acuities will be recorded (SOR will be used if the subject is wearing monovision).
- A gross assessment of lens surface will be made:
  - Overall lens surface quality/wettability (acceptable / unacceptable)
  - Comments, if applicable
- Lens fit will then be assessed and graded according to the guidelines detailed in CVI Grading scales (see Appendix 2).
  - Lens centration (0.1mm steps)
  - Corneal coverage (Yes / No / Borderline)
  - Post-blink movement (0.1mm steps)
  - Mobility rating (0.50 steps)
  - Overall lens movement (-2 to +2 scale)
  - Overall lens fit acceptance and investigator reason, if unacceptable (0.25 steps). Video will be recorded in the event of poor fit.
- The subject will remove the study lenses which will be retained for return to the Sponsor.
- Slit lamp biomicroscopy will be assessed according to the guidelines set out in the CVI Grading scales (Appendix 2)
- Subjects will undergo washout with saline solution.

## Pair 2 Dispensing

- The second study pair of contact lenses will be selected by the investigator according to the randomization table (Appendix 3) for insertion by the subjects. Subjects will be dispensed the lens power matching that of Pair 1.
- Lenses should be allowed to settle for 10 minutes.
- An initial fit assessment will be made to ensure lens fit is acceptable (Y/N). The subject should be discontinued and exited if the lens fit is found unacceptable and the primary reason for poor fit recorded on the CRF and video footage of the fit collected.
- Monocular and binocular **HIHC** and **HILC** distance logMAR visual acuities will be recorded (SOR will be used if the subject is wearing monovision).
- Subjective responses will be collected per the Post-Settling Questionnaire (Appendix 4), including:

- Lens insertion
  - Comfort satisfaction & comfort rating (6-point Likert & 100-point scales)
- A gross assessment of lens surface will be made:
  - Overall lens surface quality/wettability (acceptable / unacceptable)
  - Comments, if applicable
- Lens fit will then be assessed and graded according to the guidelines detailed in CVI Grading scales (see Appendix 2).
  - Lens centration (0.1mm steps)
  - Corneal coverage (Yes / No / Borderline)
  - Post-blink movement (0.1mm steps)
  - Mobility rating (0.50 steps)
  - Overall lens movement (-2 to +2 scale)
  - Overall lens fit acceptance and investigator reason, if unacceptable (0.25 steps). Video will be recorded in the event of poor fit.
- Information for Safety for contact lens wear during the clinical study as described in the section 5.6 will be reviewed with each subject.
- The subject must have a minimum of 8 hours of exposure in the lens on at least 2 days before their next study visit.
- The subject will be dispensed adequate lenses (including spares) to last them until the next study visit.
- The subject will be discharged and scheduled to return for Visit 2 within the required study visit window.

#### 7.5.4 Visit 3 – Pair 2 Follow-up Visit 2 days(+2 days) & Exit

*Subjects will be asked to wear lenses for at least 3 hours prior to the visit appointment..*

- The following information will be collected from the subject by the investigator:
  - Wear time at visit (hours).
  - Time of insertion and removal daily since last visit, (to calculate average time and maximum wear time(hours)).
  - Time of day lenses become uncomfortable, if at all, i.e. average comfortable wear time (hours).
- Subjective responses will be collected per the Bilateral Follow-up Questionnaire (Appendix 5), including:
  - Overall satisfaction (6-point Likert & 100-point scales)
  - Comfort & comfort rating (6-point Likert & 100-point scales)
  - Comfort (insertion) (6-point Likert & 100-point scales)

- Comfort (end of day) (6-point Likert & 100-point scales)
  - Dryness (freq/severity/bothersomeness) (5-point Likert scales)
  - Stinging/burning (freq/severity/bothersomeness) (5-point Likert scales)
  - Itchiness (freq/severity/bothersomeness) (5-point Likert scales)
  - Scratchy/gritty (freq/severity/bothersomeness) (5-point Likert scales)
  - Lens movement/awareness (freq/severity/bothersomeness) (5-point Likert scales)
  - Handling (6-point Likert & 100-point scales)
    - Insertion (freq/severity/bothersomeness) (5-point Likert scales)
    - Removal (freq/severity/bothersomeness) (5-point Likert scales)
    - Lens holding/handling (freq/severity/bothersomeness) (5-point Likert scales)
  - Vision (6-point Likert & 100-point scales)
    - Driving at night (6-point Likert & 100-point scales)
- Monocular and binocular **HIHC** and **HILC** distance logMAR visual acuities will be recorded (SOR will be used if the subject is wearing monovision).
- A gross assessment of lens surface will be made:
  - Overall lens surface quality/wettability (acceptable / unacceptable)
  - Comments, if applicable
- Lens fit will then be assessed and graded according to the guidelines detailed in CVI Grading scales (see Appendix 2).
  - Lens centration (0.1mm steps)
  - Corneal coverage (Yes / No / Borderline)
  - Post-blink movement (0.1mm steps)
  - Mobility rating (0.50 steps)
  - Overall lens movement (-2 to +2 scale)
  - Overall lens fit acceptance and investigator reason, if unacceptable (0.25 steps). Video will be recorded in the event of poor fit.
- The subject will remove the study lenses which will be retained for return to the Sponsor.
- Slit lamp biomicroscopy will be assessed according to the guidelines set out in the CVI Grading scales (Appendix 2)
- Subjects will complete the Preference Questionnaire (Appendix 6)
  - Comfort Preference
  - Vision Preference
  - Handling Preference
- Exit visual acuities (logMAR) with baseline sphero-cylindrical refraction.
- The subject will be discharged and will sign the exit statement.

### 7.5.5 Summary of Visits and Procedures

Table 2 summarizes the visits and procedures for the study.

**Table 2: Summary of Visits and Procedures**

	Visit 1a Screening/ Baseline	Visit 1b Pair 1 Dispense	Visit 2 Pair 1 Follow-up & Pair 2 Dispense	Visit 3 Pair 2 Follow-up & Exit
Informed consent	✓	-	-	-
Meet inclusion/exclusion criteria	✓	-	-	-
History at baseline	✓	-	-	-
Demographics	✓	-	-	-
Wearing time	✓	-	✓	✓
HVID / palpebral aperture size	✓	-	-	-
Auto-refraction & keratometry	✓	-	-	-
Sphero-cylindrical refraction	✓	-	-	-
HIHC & HILC VAs with sph-cyl refraction	✓	-	-	-
Slit lamp biomicroscopy	✓	✓*	✓	✓
Instillation of lens at office	-	✓	✓	-
Subjective Questionnaire	-	✓	✓	✓
Lens surface assessment	-	✓	✓	✓
Lens fit assessments	-	✓	✓	✓
Spherical over-refraction (SOR)	-	✓	-	-
HIHC & HILC Distance VAs (with CLs)	-	✓	✓	✓
Lens Preference Questionnaire	-	-	-	✓
Exit VAs	-	-	-	✓
Study Exit	-	-	-	✓

\* Slit lamp biomicroscopy to be repeated to re-confirm eligibility in the event Visit 1b does not occur on the same day as Visit 1a

## 8 Adverse Events and Device Deficiencies

### 8.1 Adverse Event Definitions

An 'adverse event' refers to any undesirable clinical occurrence in a participant, whether it is considered to be device-related or not. Adverse events (AE) may be classified as 'unanticipated adverse device effects,' 'serious adverse events,' 'significant adverse events,' or 'non-significant adverse events,' as defined below.

Classification	Definition
Serious Adverse Event	Those events that are life-threatening, or result in permanent impairment of a body function, or permanent damage to a body structure or necessitate medical (therapeutic) or surgical intervention to preclude permanent impairment of a body function or permanent damage to a body structure.
Significant Adverse Event	Those non-serious adverse events that occur with contact lens usage that are not sight-threatening but are usually symptomatic and may warrant therapeutic management and /or temporary or permanent discontinuation of contact lens wear.
Non-Significant Adverse Events	Those less severe non-serious adverse events that occur with contact lens usage that are not sight-threatening, may or may not be symptomatic and may warrant palliative management, such as ocular lubricants or temporary interruption of contact lens wear.
Unanticipated Adverse Device Effect	Adverse events in a clinical trial that were not previously identified in the protocol in terms of nature, severity, or degree of incidence. An Unanticipated Serious Adverse Device Effect is an unanticipated adverse event that is serious in nature and caused by or associated with the device and is considered reportable.

AE classification, coding (for reporting to the Sponsor) and examples are provided in the following table of Contact Lens Adverse Event Classification and Reporting table:

Code	Condition	Reporting
Serious Adverse Events		
01	Presumed infectious keratitis or infectious corneal ulcer	Notify Sponsor as soon as possible, within 24 hours ; IRB reporting as per requirements
02	Permanent loss of $\geq$ 2 lines of best spectacle corrected visual acuity (BSCVA)	
03	Corneal injury that results in permanent opacification within central cornea (6mm)	
04	Uveitis or Iritis (e.g. presence of anterior segment inflammation as described in ISO 11980, Annex B)	
05	Endophthalmitis	
06	Hyphema	
07	Hypopyon	
08	Neovascularization within the central 6mm of cornea	
00	Other serious event	
Significant Adverse Events		
11	Peripheral (outside central 6mm), non-progressive, non-infectious ulcer	Notify Sponsor as soon as possible, within 5 working days ; IRB reporting as per requirements
12	Symptomatic corneal infiltrative event	
13	Superior epithelial arcuate lesions (SEALs) involving epithelial split	
14	Corneal staining $\geq$ dense coalescent staining up to 2mm in diameter (e.g. moderate, ISO 11980 grade 3)	
15	Corneal neovascularization $\geq$ 1.0mm vessel penetration (e.g. $\geq$ ISO 11980 Grade 2), if 2 grade change from baseline	
16	Any temporary loss of $\geq$ 2 lines BSCVA for $\geq$ 2wks	
17	Any sign and/or symptom for which subject is administered therapeutic treatment or which necessitates discontinuation of lens wear for $\geq$ 2 weeks	

10	Other significant event	
----	-------------------------	--

Non-significant Adverse Events		
21	Conjunctivitis (bacterial, viral or allergic)	
22	Papillary conjunctivitis if $\geq$ mild scattered papillae/follicles approximately 1mm in diameter (e.g. ISO 11890 Grade 2), if 2 grade change from baseline	
23	Asymptomatic corneal infiltrative events	
24	Any sign and/or symptom for which temporary lens discontinuation for $> 1$ day is recommended (if not already classified)	
20	Other sign and/or symptom warranting classification as a non-significant adverse event	Notify Sponsor as soon as possible, within 5 working days ; IRB reporting as per requirements

